### **Secondary Biochemical Endpoints**

- Plasma levels of citrulline, Arginine and other amino acid intermediates will be evaluated at baseline, 2-hours, 12-hours, and study days 2, 4, 8, and 10. The PK-PD associations will be evaluated especially to explore associations with outcomes of interest as per clinical endpoints.
- Plasma levels of arginine at baseline, 2-hours, 12-hours, and study days 2, 4, 8, and 10.
- Plasma levels of ornithine at baseline, 2-hours, 12-hours, and study days 2, 4, 8, and 10.
- Plasma NOx levels at baseline, 2-hours, 12-hours, and study days 2, 4, 8, and 10.

### **Statistical Method for the Citrulline Biochemical Efficacy Endpoint**

The analysis team will provide the means and standard deviations for citrulline plasma levels separately for each treatment group and for each assessment periods. A generalized linear mixed model (GLMM) with appropriate link function (i.e., identity link for continuous outcome) will be used to compare these plasma amino levels across the two intervention groups. The model will examine how the treatment means differ (i.e., main treatment effect), how treatment means change over time (i.e., main time effect), and how differences between treatment means change over time (i.e., treatment-by-time effect). We will calculate the point estimates and their respective confidence intervals for the changes in patients' citrulline plasma levels for each intervention group and for the difference in the estimated change between intervention groups. Additionally, we will present the p-value of the difference in point estimates between intervention groups.

### **Statistical Method for the Biochemical Efficacy Endpoints (arginine, ornithine, and NOx)**

For the secondary biochemical endpoint arginine, ornithine, and NOx, we will follow the same analytical method described to analyze plasma levels of citrulline.

## **Secondary Safety Endpoints**

- Hemodynamic status (worst vasopressor dependency index through day 10)
- Number of reported adverse events

### **Statistical Method for the Safety Endpoint (Hemodynamic status)**

The vasopressor dependency index (VDI) is a continuous variable calculated by dividing vasopressor index (summation of all pressors) by the mean arterial blood pressure (MAP). VDI will be calculated at baseline (immediately before start of the infusion), 2 hours after completion of the bolus, and every 4 hours during the infusion. We will report descriptive statistics (mean  $\pm$  SD) of baseline and worst VDI separately for each treatment group. Worst VDI will be compared between groups using an analysis of covariance (ANCOVA) with the baseline VDI as the covariate.

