6.2 Inclusion Criteria

Participant eligibility is determined based on the selection of criteria detailed below:

1. Age 18-65 years.
2. Clinical evidence of COVID-19 (SARS-CoV2) infection, defined as a positive COVID-19 laboratory test plus evidence of an acute hypoxic respiratory illness requiring oxygen.
3. Admitted and transferred to floor without intubation.

6.3 Exclusion Criteria:

Patients meeting any of the following criteria will not be eligible for participation in the study:

1. No consent/inability to obtain consent
2. Patient, surrogate, or physician not committed to full support
3. Malignant or other irreversible condition and estimated 28-day mortality $\geq 50\%$
4. Moribund patient not expected to survive 48 hours (as defined by primary medical team) from start of study infusion
5. End-stage Liver Disease as defined by Child-Pugh Score > 9
6. Currently enrolled in, or participated in another study of an investigational compound within the last 30 days
7. Pregnant female, or female who is breast feeding
8. Allergy to L-citrulline or arginine or any citrulline- or arginine-containing product
9. Patient not otherwise suitable for the study in the opinion of any of the investigators
10. Requirement for intubation and invasive mechanical ventilation before study enrollment

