7.1.3 Hemodynamic Assessments

Blood pressure measurements will represent a major component of the hemodynamic assessments. Vasopressor dosages in critically ill patients will also form a significant component of these assessments. Vasopressor Dependency Index (VDI) will be used as the measure of hemodynamic assessment. VDI is a continuous variable calculated by dividing vasopressor index (summation of all pressors) by MAP. VDI will be calculated at baseline (immediately before start of the infusion), again 2 hours after completion of the bolus, and every 4 hours during the infusion. Any cases where the VDI increases by more than 20% from baseline will result in interruption of the study infusion and review by the safety officer in an expedited fashion.

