9.3 Pre-Existing Conditions

Pre-existing conditions that are present before the start of the study infusion will be considered concurrent medical conditions and should NOT be recorded as adverse events. However, if the subject experiences a worsening or complication of such a concurrent condition, the worsening or complication may be recorded as an adverse event at the discretion of the investigator.

The following are clinical outcomes of an acute hypoxemic respiratory illness progressing to critical illness due to COVID-19 infection (SARS-CoV2), and as such, will not be considered as adverse events:

1. Respiratory: decreased SaO₂/FiO₂ or PaO₂/FiO₂, mechanical ventilation, acute lung injury or acute respiratory distress syndrome (ARDS), or respiratory failure
2. Hepatic: hepatic injury or liver dysfunction; increased bilirubin
3. Renal: renal failure, need for dialysis, increased creatinine
4. Coagulation: disseminated intravascular coagulation (DIC), thrombocytopenia
5. Central Nervous System (CNS): acute mental status changes (not associated with localizing neurological signs)

6. Vital Signs: tachypnea, hypothermia, hyperthermia, tachycardia

Cardiovascular function will be systematically collected as both MAP and vasopressor dosages. VDI will be calculated at baseline (immediately before start of the infusion), again 60 minutes after completion of the bolus, and every 4 hours during the infusion. Any cases where the VDI increases by more than 33% from baseline will be considered an adverse event and submitted for review by the safety officer in an expedited fashion.

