The risks of citrulline are theoretical. In previous studies enrolling hundreds of humans, no serious adverse events have been attributed to either oral or intravenous citrulline. Citrulline may increase NO production and exacerbate hypotension. Arginine, a product of citrulline via the urea cycle, has been reported to exacerbate hypotension. The blood pressure of every participant in this study will be monitored closely throughout the study and especially during the infusion. As these patients will be cared for in a hospital unit or ICU, blood pressure measurements will be taken per hospital unit or ICU protocol. Hypotension, as measured by vasopressor dependency index (VDI) represents an *a priori* endpoint of the study. VDI will be calculated 2 hours after the bolus and daily. Any worsening of VDI by 33% or more will prompt review by the safety monitor. Although it is likely to reduce organ dysfunction by attenuating inflammation and oxidative stress, daily labs will be monitored for adverse events on organ functioning. The citrulline will be administered in a small volume of 5% dextrose water (30 mL bolus followed by ~15 mL/hr). This small amount of dextrose should not dramatically increase blood sugar levels in these patients and as such, should pose minimal risk. Furthermore, any event which the investigator or primary team is concerned may be related to study drug administration will be reported as an adverse event. Participants will be monitored for any signs of allergic reaction, including new wheezing, itching and/or rash. Blood pressure, which might fall during severe allergic reactions such as anaphylaxis, will be closely monitored in the hospital or ICU setting with treatment available as needed.

The placebo will be a small volume of 5% dextrose water (30 mL bolus followed by ~15 mL/hr). Although administration of dextrose in theory could raise blood sugar levels, the small volume will result in little dextrose being administered which should not significantly increase blood sugar levels in these patients and as such, should pose minimal risk. In addition, blood sugar levels are routinely measured and monitored closely as part of routine care in intensive care unit patients, especially those with severe sepsis.

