APPENDIX A: Schedule of Events

Measurement	Day 0 (baseline)	Day 1	Day 2	Day 3	Day 4	Day 5	Day 6	Day 7	Day 8	Day 9	Day 10	Day 11	Day 12-DC	Day 28 ^e Follow-up	Day 60 ^e Follow-up
Informed Consent	X														
Demographics- Hx & Px	X														
Eligibility Assessment	X														
Pregnancy Test	Xc														
Study Drug Administration		X	X	X	X	X	X	X	X	X					
Vital Signs		X	X	X	X	X	X	X	X	X	X	X	X		
Mean Arterial Pressure		Xa,b,d	X	X	X	X	X	X	X	X	X	X			
Vasopressor Dosages		Xa,b,d	X	X	X	X	X	X	X	X	X	X			
Basic Metabolic Panel		A	A	A	A	A	A	A	A	A	A	A			
CBC		A	A	A	A	A	A	A	A	A	A	A			
LFTs		Ab	A	A	A	A	A	A	A	A	A	A			
D-dimer blood draw		Xa,b	X		X		X		X		X		X		
CRP		Xa,b	X		X		X		X		X		X		
5 ml blood for citrulline etc.		Xa,b	X		X		X		X		X				
SaO2/ FiO2 ratio		X	X	X	X	X	X	X	X	X	X	X			
PaO2		X	X	X	X	X	X	X	X	X	X	X			
ABG		A	A	A	A	A	A	A	A	A	A	A			
Hospital status		X	X	X	X	X	X	X	X	X	X	X	X	X	X
ICU status		X	X	X	X	X	X	X	X	X	X	X	X	X	X
Non-invasive ventilation status		X	X	X	X	X	X	X	X	X	X	X			
Invasive ventilation status		X	X	X	X	X	X	X	X	X	X	X			
ConMed Review		X	X	X	X	X	X	X	X	X	X	X	X	X	X

Adverse Event Review		X	X	X	X	X	X	X	X	X	X	X	X	X	X	X
----------------------	--	---	---	---	---	---	---	---	---	---	---	---	---	---	---	---

a= measurement should be recorded or performed at hours 0, 2 and 12

b= Day 1 hour 0 samples/procedure must be collected/recorded before study drug is administered.

c= only perform if patient is of childbearing potential

d= must be collected 15 minutes prior to administration of study medication

e= Day 28 and Day 60 are telephone follow ups

X= Study Procedure A= Standard of Care

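### Worst VDI is 0 at any blood pressure while no vasopressor runs, so it cannot register hypotension managed without pressors; its safety triggers conflict and cannot be computed from a zero baseline

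*SAP*

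**What the plan says.** **Definition.** The SAP's section on hemodynamic status states that VDI "is a continuous variable calculated by dividing vasopressor index (summation of all pressors) by the mean arterial blood pressure (MAP"). Protocol 7.1.3 and 10.5 give the same formula.

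**Role.** The protocol synopsis and SAP Table 2 call worst VDI through Day 10 the primary safety variable. Table 2 is nevertheless titled as secondary safety endpoints, and the SAP lists worst VDI again under Secondary Safety Endpoints. Protocol 11.5 gives its purpose: "Hypotension, as measured by vasopressor dependency index (VDI") is presented there as a prespecified endpoint. The analysis is an ANCOVA of worst VDI on baseline VDI.

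**Triggers.**
- Protocol 7.1.3: "Any cases where the VDI increases by more than 20% from baseline will result in interruption of the study infusion and review".
- Protocol 9.3: "Any cases where the VDI increases by more than 33% from baseline will be considered an adverse event", also with expedited review.
- Protocol 11.5: "Any worsening of VDI by 33% or more will prompt review by the safety monitor".

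**Timing.** Protocol 7.1.3, 10.5, 11.5 and the SAP place the first post-bolus VDI at 2 hours. Protocol 9.3 says "again 60 minutes after completion of the bolus". Later values are four-hourly in 7.1.3, 9.3 and the SAP, but daily in 11.5. The Day 1 schedule for MAP and pressor doses in Appendix A reads "a= measurement should be recorded or performed at hours 0, 2 and 12".

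**Entry.** Inclusion criterion 3 is "Admitted and transferred to floor without intubation". Pressor use at entry is neither required nor excluded.

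**The concern.** Protocol 11.5 names hypotension, through increased nitric oxide, as the theoretical risk of citrulline. A measure that moves only once a pressor is running says nothing about a fall handled with fluids, by pausing the infusion or by observation. In a population recruited from the floor, that may be how early hypotension is handled. Between arms, such falls would appear only in adverse-event counts, and each investigator would decide what counts as hypotension without a shared MAP level.

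Separately, a rule for interrupting dosing should give one answer at the bedside. Here three sections give different review thresholds, two give different post-bolus times, and none says what to do when the baseline is 0.

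**Working it through.** The documents give no power, pressor rate or expected VDI, so there is no stated figure to reproduce. The inputs are the VDI formula, the three thresholds and the 66 patients to be accrued. A starting MAP of 75 mmHg is illustrative.

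**1. No pressor.** VDI = P/MAP with P = 0. At MAP 75, 0/75 = 0; at MAP 55, 0/55 = 0. The fall leaves no trace in the variable.

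**2. Fixed pressor dose.** VDI after / VDI before = (P/MAP₁)/(P/MAP₀) = MAP₀/MAP₁.
- A 20% rise: 75/1.20 = 62.5 mmHg, a MAP fall of 16.7%.
- A 33% rise: 75/1.33 = 56.4 mmHg, a MAP fall of 24.8%.

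A patient between those two pressures is interrupted and reviewed under 7.1.3, but reaches no VDI review threshold under 9.3 or 11.5.

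**3. Zero baseline.** The percentage rise is (VDI_t − 0)/0, which has no value. Read as a multiple, the threshold is 1.20 × 0 = 0 or 1.33 × 0 = 0, so any pressor start fires the rule. The documents choose neither reading.

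**4. Who is affected.** No baseline pressor rate is given, so take 0%, 5% or 10% as an assumed range. Patients on pressors at baseline: 66 × 0 = 0, 66 × 0.05 = 3.3, 66 × 0.10 = 6.6. The 20%-versus-33% conflict can therefore concern about 0, 3 or 7 patients. The other 66, 63 or 59 have no computable percentage.

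**5. Effect on the comparison (illustration; all rates assumed).** Take 30 per arm, every baseline VDI 0 and true hypotension of 10% versus 40%. Let pressor-treated episodes have the same lognormal VDI distribution in both arms, and compare worst VDI with a two-sample t-test. That is what the ANCOVA reduces to when every baseline is 0, because the baseline term cannot then be estimated. Over 4,000 simulated trials per scenario, power was:

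| Episodes managed without pressors | Worst VDI | Fisher's test on hypotension itself |
|---|---|---|
| None | 60% | about 70% |
| Half | 31% | about 70% |
| 80% | 5% | about 70% |
| All | 0% | about 70% |

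The last row follows from step 1 whatever rates are assumed.

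**6. What a MAP comparison could show.** With 33 per arm, the 95% CI half-width is t(0.975, 63) × SD × √(1 − r²) × √(2/33). With SD 8 and baseline correlation 0.5 this is 3.4 mmHg; with SD 12 and correlation 0.3 it is 5.6 mmHg. With 30 per arm the range is 3.6 to 5.9 mmHg. SD and correlation are assumed, and no power is claimed.

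**The case against.** The strongest reply is that this is a limit of one variable and not a hole in safety monitoring. Much of that stands:
- Hypotension is a systematically collected adverse event (Protocol 9.1), is not among the disease outcomes exempted in 9.3, and is tabulated by severity and arm under the SAP.
- It is part of the safety look after 20 patients (10.7), and the safety officer can act on significant hypotension (11.4).
- Two hold rules do not depend on VDI. Under 9.0 the infusion is withheld for any suspected drug-related event until it is evaluated; under 5.2.3 it is stopped for a significant safety concern.

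A reader might therefore infer too much from the formula: that the trial cannot see pressor-free hypotension, or that interruption for patients starting at zero depends only on how staff read a percentage of zero. The documents support neither. What remains is that these routes share no MAP cut-off and that no MAP comparison between arms is planned.

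It can also be said that the 20% and 33% rules are tiers, one for interruption and one for adverse-event classification, and that following 7.1.3 meets all three review thresholds. That is workable, but no section says so, and it leaves the zero baseline and the 60-minute check unresolved.

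Finally, floor entry does not prove zero baselines, and 5.1.1 mentions delivery to the ICU. That is fair: the share of zero baselines is an inference.

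**Conclusion.** The point holds and is worth fixing, but it does not threaten the efficacy primary. Three things follow directly from the text: VDI is 0 without a pressor; the review thresholds and post-bolus times disagree; and a percentage rise from 0 cannot be computed. That most patients start at 0 is probable, not documented. The threshold conflict touches only patients already on pressors, about 0 to 7 of 66 on the assumed rates. The zero-baseline gap would touch the rest.

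Worst VDI carries the label of primary safety variable, but the SAP analyzes it among secondary safety endpoints, so the label should not be given more weight than that.

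Two further inferences are not supported. One is that the ANCOVA is the wrong test: nothing here shows that, and it can stay. The other is that early exit biases a lowest-MAP comparison. Protocol 5.1.2 has patients leave the study once weaned off oxygen, while 11.5 says data collection continues after the drug stops. Until those are reconciled, no such bias can be claimed.

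**What to change.** 1. **Triggers (Protocol 7.1.3, 9.3, 11.5).** Adopt one review and interruption threshold and the 2-hour check already in the SAP and Appendix A. At zero baseline, make the trigger any new vasopressor start, or a MAP fall prespecified by the safety officer. Use the same MAP rule to define the hypotension adverse event and for the 20-patient look or, if that look has passed, for the final tabulation.
2. **VDI convention (SAP and synopsis).** State that VDI is 0 when no pressor runs, for every patient, through Day 10. Protocol 5.1.2 ties the conversion to critical illness, while 7.2.2 supports a value for all. Correct the synopsis, whose statistical section limits worst VDI to the first six days.
3. **MAP comparison (SAP).** Add a descriptive between-arm ANCOVA of the lowest scheduled CRF MAP on baseline MAP, outside the Hochberg family. Use the 2-hour, 12-hour and Day 2 readings as the common window, and also summarize lowest MAP through Day 10, because the short window misses Days 3 to 10. Report the proportion receiving any vasopressor alongside, since pressors hold MAP up. Falls between readings will still be missed. Reconcile 5.1.2 with 11.5 on data after early exit.
4. **Keep the planned VDI ANCOVA.**

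**Cost.** Item 1 needs a short amendment with IRB review, because it changes a dosing rule. Items 2 and 3 need SAP and synopsis wording, the reconciling line in the protocol and one extra descriptive table; no new data are collected. Protocol v3.0 is dated June 2021 and database lock was planned for September 2021, so the dosing amendment may reach few patients. If enrollment is complete, only the hypotension definition, the VDI convention and the MAP analysis still apply.

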### **Statistical Method for the Secondary Safety Endpoint (Adverse events)**

All reported adverse events will be tabulated and categorized by level of severity and reported by treatment groups. Adverse events will be evaluated further where causality is attributed as suspect.

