## **STUDY ASSESSMENTS**

The assessment of efficacy will include collection of plasma for analysis of citrulline and arginine levels at 2 hours, 12 hours, and the alternating morning of study days the infusion is running for a maximum of

10 days, i.e., on days 2, 4, 6, 8 and 10. A patient will exit the study early if they have been weaned off all oxygen support before 10 days. Additional efficacy measures will include clinical outcomes, including progression of acute lung injury and lengths of hospital and ICU stay.

The assessment of safety will include collection of hemodynamic measurements at least every 4 hours on a hospital unit and--if a patient is critically ill in an ICU--hourly while the study material is infusing and for 12 hours after completion of the infusion in each patient. Hemodynamic measurements will be converted to a vasopressor dependency index for analysis if a patient becomes critically ill. Adverse event reporting will also serve as a means of safety analysis. Additional safety measures will be biochemical and hematologic laboratory measurements. The biochemical laboratory measurements, including liver function tests (ALT, AST, bilirubin, alkaline phosphatase), kidney function tests, D-dimer tests, CRP and electrolytes, along with hematologic laboratory measurements, including complete blood count and platelet count, will be collected when available for any study day in order to evaluate for adverse events.

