**Table 2: Secondary Safety Endpoints**

Safety Variables:	

1. Primary safety variable is hemodynamic status, specifically worst vasopressor dependency index through day 10.

2. Incidence of reported adverse events.

Safety Evaluations:	
In addition to vasopressor dependency index, the following laboratory values will be used for safety assessment at baseline and daily through study day 4 when available.
 

1. Complete blood count with platelets

2. Basic Metabolic profile, including renal function

3. Liver function tests, including SGOT, SGPT, total bilirubin, and alkaline phosphatase

 
Adverse events will be recorded prospectively, including incidences of hypotension, hepatitis (i.e., the elevation of liver enzymes), and injection site reactions.

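### The SAP specifies no by-arm summary of on-treatment laboratory values, so a non-fatal renal or coagulation imbalance may be under-reported

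*SAP*

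**What the plan says.** **Safety outputs.** Under Secondary Safety Endpoints the SAP lists worst VDI through day 10 and "Number of reported adverse events". Worst VDI is compared by ANCOVA with baseline VDI as covariate. For adverse events the method is: "All reported adverse events will be tabulated and categorized by level of severity and reported by treatment groups". The Interim Analyses section plans one safety look after 20 patients, at VDI and hypotension.

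**What counts as an adverse event.** Protocol 9.3 lists outcomes of illness progressing to critical illness, "and as such, will not be considered as adverse events". The list includes "Renal: renal failure, need for dialysis, increased creatinine" and "Coagulation: disseminated intravascular coagulation (DIC), thrombocytopenia".

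**Laboratory values.** SAP Table 2 names blood count with platelets, metabolic panel with renal function, and liver tests, and says that "the following laboratory values will be used for safety assessment at baseline and daily through study day 4 when available". The protocol's study summary has the same limit. SAP Study Assessments differs: laboratory measures, including "kidney function tests, D-dimer tests, CRP and electrolytes", "will be collected when available for any study day in order to evaluate for adverse events". Appendix A of the protocol schedules the three panels as standard of care on days 1 to 11, and D-dimer as a study procedure. The only laboratory summary that the SAP specifies by arm is at baseline (Analysis of Demographics and Baseline Characteristics).

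**The concern.** Exempting expected complications from adverse event reporting is reasonable in severe COVID-19, provided they are compared between arms in some other way. For the respiratory items in 9.3 this largely happens, because intubation, ventilation and oxygen therapy are endpoints. Deaths enter hospital mortality. Protocol 9.1 has hypotension, liver-enzyme elevation and injection site reactions collected systematically as adverse events. Non-fatal renal and coagulation events have no such route. They are not endpoints, they are not on the 9.1 list, and the laboratory values that would show them have no specified on-treatment output.

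Safety is a stated aim of the trial, and protocol 11.4 plans no formal data safety monitoring board. When a complication is expected in the disease, a difference in its frequency is hard to see one patient at a time; a by-arm table is where it would show.

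**Working it through.** The plan has no figure of its own on this point. The check sets the rules side by side and counts scheduled days.

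**Step 1: routes by which a non-fatal renal or coagulation event could appear by arm**

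- *Worst VDI and the interim look:* these cover haemodynamics only.
- *Adverse event table:* excluded by default under 9.3. A case can enter if judged clinically important and unexpected (9.0), if it is a new and clinically significant laboratory abnormality (9.2), or if someone suspects the drug (11.5). Section 9.2 adds that an abnormality consistent with a current diagnosis need not count. The documents do not say whether 9.2 or 9.3 prevails, or how 9.3 interacts with the serious adverse event definition in 9.4.
- *Discontinuations by reason (SAP, Patient Disposition):* a case appears only if it led to stopping and was classed under one of the listed reasons.
- *Daily review by the safety officer (11.4):* this looks at individual patients and gives no comparison.
- *On-treatment laboratory tables:* none specified. Protocol 10.2 promises treatment-specific summary tables in general terms but leaves detailed methods to the SAP.

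The SAP collects laboratory values on any study day in order to look for adverse events, and that leads back to the 9.3 entry rule.

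**Step 2: the day-4 window**

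- Metabolic panel, blood count and liver tests are marked on days 1 to 11 in Appendix A: 11 days.
- Inside the Table 2 window, days 1 to 4: 4/11 = 36%.
- Outside it, days 5 to 11: 7/11 = 64%.
- With the infusion running through day 10 (protocol 5.2), days 5 to 10 are 6/10 = 60% of a full course. Appendix A marks study drug on days 1 to 9; on that count the share is 5/9 = 56%.

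**Step 3: D-dimer**

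Hour 0 is baseline. Hours 2 and 12 and days 2, 4, 6, 8 and 10 give 2 + 5 = 7 post-baseline time points through day 10. Four fall by day 4 and three after it. Table 2 lists none of them, although Study Assessments treats D-dimer as a safety measure.

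**Step 4: size of a missed imbalance**

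This would need renal and coagulation event rates and the fraction recorded as adverse events. The documents give neither, so no figure is offered.

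**The case against.** The strongest reply is that the gap is smaller than it looks.

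- *Cases can reach a by-arm table.* An event admitted under 9.0, 9.2 or 11.5 becomes an adverse event, and the SAP tabulates those by treatment group. This stands. A reader might infer from 9.3 that renal and coagulation harm cannot appear in any comparison of the arms; the documents do not support that. What remains is that entry depends on individual judgement, generally blinded, under rules whose order of precedence is not stated.
- *Laboratory collection does not end on day 4.* This also stands. Table 2 limits which values are used for safety, while Appendix A and Study Assessments carry collection further. The fault is an inconsistency about use, and for that reason it is cheap to repair.
- *A table that is not named is not excluded.* Protocol 10.2 promises treatment-specific summaries, and the SAP describes itself as giving guidelines that are only sometimes specific. Laboratory tables may well be produced. But the SAP is where detailed methods belong, and its explicit limit is day 4.
- *The percentages count schedule days.* They do not count patients, values or events. Day 11 follows the infusion, and patients weaned off oxygen stop the drug early, so days 5 to 10 are not exposure for everyone. This stands; the figures describe the window and nothing more.

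**Conclusion.** The point holds as a gap in the specified safety output. Two written rules, the 9.3 exemption and the day-4 limit, followed together leave non-fatal renal and coagulation harm without a reliable comparison between arms. Under-reporting may result. How much depends on how investigators apply 9.2 and 9.3, which the documents do not settle, and on event rates they do not give. It would go too far to say that an excess would be invisible or to put a power loss on it.

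The measurable part is the window: 36% of scheduled panel days inside it, and none of the 7 post-baseline D-dimer time points through day 10 listed. These counts rest on Appendix A as scheduled; actual draws will be fewer where standard of care does not require them. The primary efficacy analysis is untouched. The change should be made before database lock.

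**What to change.** In SAP Table 2:

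- Replace day 4 with day 11, in line with Appendix A and Study Assessments, and note the departure from the protocol summary.
- Add D-dimer on its own schedule.

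Under Secondary Safety Endpoints, add descriptive by-arm tables:

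- Baseline-to-worst change for creatinine, platelets, D-dimer and bilirubin. ALT and AST are optional, because liver-enzyme elevation is already collected as an adverse event.
- Number and percent with marked worsening on a grading scale that the sponsor names in advance, with the risk difference and its exact 95% confidence interval.
- Number of patients with a post-baseline value, and number of measurements per patient.
- Counts of dialysis and DIC only if the case report form captures them; Appendix A has no row for either.

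State that these tables carry no p-values and stand outside the Hochberg family. The 9.3 exemption need not change.

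The cost is SAP wording and a few tables, with no new data, visits or staff. The drawback is that standard-of-care values are incomplete and more numerous in patients who stay longer, so a worst value depends partly on how often a patient was measured. With 66 patients split 1:1, one patient is 1/33 = 3 percentage points of an arm, and only a large imbalance would show.
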